6.1 Flowchart

The formation of the populations will be described by a Consort-Flowchart.

6.2 Descriptive Analysis

The results of descriptive analyses will be shown in common tables for the populations OP, ITT and mITT where quantitative parameters will be shown with number (N), number of missings (miss), mean, standard deviation, minimum, maximum and quartiles (q1, q2 = median and q3). Qualitative parameters will be presented with number (N), number of missings (miss), total and relative frequency.

6.3 Statistical Analysis

6.3.1 Primary Endpoint

The primary endpoint, the change of the mean daytime physical activity between baseline (before treatment start) and post-treatment week 12, will be calculated and analyzed by t-test or Wilcoxon-test, depending from the distribution of the data (normal or not). The significance level will be set to $\alpha = 0.05$, the test will be performed two-sided.

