**9.3 Variables**

**9.3.1 Primary Variable**

- Change of mean daytime physical activity between baseline (before treatment start) and post-treatment week 12

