### **9.5 Study Size**

Observational research is exploratory in nature and there are no pre-specified hypotheses to be tested. Hence, there is no need for power calculation. The primary endpoint in this study is derived from an activity tracking device.

In the literature, no data on actigraphy in HCV patients suffering from fatigue are available that would allow statistical sample size calculation focusing on the precision of estimation of the primary endpoint.

On the other hand, the patient selection criteria only allow recruitment of a restricted number of patients in a justifiable period of time. We assume that a total of 100 patients are sufficient to provide stable results regarding investigation of the study objectives.

The planned study size of 100 will have 80% power to detect a change from baseline of the effect size 0.29 using a two-sided one-sample t-test with a significance level of 5%.

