## **9.7 Data Analysis**

All data will be analyzed by descriptive statistical methods.

Quantitative data (e.g. the primary variable) will be analyzed by the statistical parameters valid N, missing N, mean, standard deviation (SD), and selected quantiles: minimum (0%), lower quartile (25%), median (50%), upper quartile (75%), and maximum (100%). If indicated by the data, an additional frequency distribution will be supplied after appropriate grouping of data.

Qualitative (e.g. achievement of SVR12 (yes/no)) and categorical variables (e.g. individual items of the FSS) will be presented by (absolute and relative) frequency distributions.

The primary variable will be tested using the one-sample t-test (two-sided) on the 5% significance level.

Two-sided 95% confidence intervals will be provided for mean daytime physical activity, FSS and sleep efficiency by visit and for the changes between start of treatment and the respective follow-up visits. A 95% confidence interval for the proportion of patients achieving SVR12 will also be calculated.

The correlation between the physical activity (assessed by the activity tracker) and the fatigue score (assessed by FSS) will be investigated by visit and for the changes between baseline and follow-up visits, using Spearman's rank correlation coefficient.

Subgroup analyses will be provided for patients who achieve / do not achieve SVR12 after treatment with 3D regimen.

All statistical analyses will be carried out by means of the SAS® package (version 9.2 or higher).

Details of planned analyses will be described in a separate statistical analysis plan (SAP).

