5.2 Analysis Populations (ITT and mITT)

The statistical analyses will be performed for the intention-to-treat population (ITT) and the modified ITT population (mITT) as well. The ITT consists of all documented patients of the overall population with treatment as intended to protocol and received study medication at least once. Additionally, mITT consists of all patients of the ITT which take part at all five visits. For ITT and mITT descriptive and safety parameters will be analyzed. Primary and secondary endpoints will be analyzed for mITT.

6 Statistical Methods

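### SAP 6.3.1 lets the data choose between t-test and Wilcoxon for the primary endpoint, against the protocol's fixed one-sample t-test; with skewed changes this rule does not hold 5% for the mean change

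*SAP*

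**What the plan says.** The primary variable in Protocol 9.3.1 is "Change of mean daytime physical activity between baseline (before treatment start) and post-treatment week 12". Protocol 9.7 names one test for it: "The primary variable will be tested using the one-sample t-test (two-sided) on the 5% significance level". Protocol 9.5 uses the same test for its power statement: "The planned study size of 100 will have 80% power to detect a change from baseline of the effect size 0.29".

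SAP 6.3.1 keeps the endpoint, the 0.05 level and two-sidedness ("the test will be performed two-sided"), but the endpoint is now "analyzed by t-test or Wilcoxon-test, depending from the distribution of the data (normal or not"). It names no normality test or threshold. It does not say whether normality is judged on the changes or on the visit values, or which Wilcoxon test is intended. It does not mention that the protocol specified something else.

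Both documents (Protocol 9.7, SAP 6.3.2) also plan 95% confidence intervals for the change in daytime activity. SAP 5.2 restricts the endpoint analysis to patients who attended all five visits: "Primary and secondary endpoints will be analyzed for mITT".

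**The concern.** There are two problems. The first is textual: the protocol fixes one test, and the SAP replaces it with a choice made after the data are seen, under a rule too loose to reproduce. Two statisticians following SAP 6.3.1 could report different primary p-values from the same dataset.

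The second is statistical. The Wilcoxon signed-rank test is a valid test of a zero centre only if the changes are symmetric. For skewed changes it tests the pseudo-median (the median of the average of two independent changes), which can differ from zero when the mean is zero. When skewness is what fails the normality check, the rule therefore abandons a test that copes well with skewness at this sample size for one whose hypothesis is altered by it.

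This is the only test with a stated alpha. Its hypothesis is left open (mean or pseudo-median), its error rate for the mean change is not controlled under skewness, and its p-value could disagree with an interval for the mean change. The power figure applies to the t-test only.

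**Working it through.** **1. The plan's own figure.** Inputs from Protocol 9.5: N=100, effect size d=0.29, two-sided 5%, one-sample t-test.

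- Noncentrality = d√N = 0.29 × 10 = 2.9, with 99 degrees of freedom and critical value 1.984.
- Power by noncentral t = 81.9%. Normal approximation: Φ(2.9 − 1.96) = Φ(0.94) = 82.6%.
- Exactly 80% needs N=96, and N=100 detects d=0.283.

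The stated 80% is reproduced, slightly on the safe side, for the t-test.

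**2. Why the signed-rank test drifts.** Take changes from a gamma distribution with shape k, centred to mean 0 (skewness 2/√k, SD √k). The pseudo-median is median[Gamma(2k)]/2 − k.

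- Skewness 1 (k=4): 7.669/2 − 4 = −0.165. Divided by the SD of 2, this is −0.083 SD.
- Skewness 2 (k=1): 1.678/2 − 1 = −0.161. The SD is 1, so this is −0.161 SD.

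The mean change is zero, yet the test sees a shift. Treating that shift like a mean shift at N=100 gives rough rejection rates. For skewness 1: Φ(0.83 − 1.96) + Φ(−0.83 − 1.96) ≈ 13%. For skewness 2: Φ(1.61 − 1.96) + Φ(−1.61 − 1.96) ≈ 36%. The shift is fixed, so the problem grows with N.

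**3. Simulation.** True mean change 0; 10,000 datasets per setting; two-sided 0.05. The SAP rule was read as: Shapiro-Wilk p<0.05, use Wilcoxon signed-rank; otherwise use the t-test. The Shapiro-Wilk criterion and the skewness values are assumptions. The SAP names no check, and Protocol 9.5 states that "no data on actigraphy in HCV patients suffering from fatigue are available" on which a sample size calculation could be based. Monte Carlo standard error is about 0.2 points at 5%.

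Rejection rates at N=100:

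| Distribution of changes | Sent to Wilcoxon | SAP rule | Fixed t-test |
|---|---|---|---|
| Normal | 4.7% | 5.0% | 4.9% |
| t with 5 df (symmetric, heavy tails) | 56.7% | 5.2% | 5.1% |
| Gamma, skewness 0.5 | 42.3% | 6.6% | 5.2% |
| Gamma, skewness 1.0 | 95.5% | 12.5% | 5.2% |
| Gamma, skewness 1.41 | 100% | 21.9% | 5.5% |
| Gamma, skewness 2.0 | 100% | 38.3% | 5.9% |

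The size of the set with all five visits is not given, so smaller sets were also run:

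| N | Skewness | SAP rule | Fixed t-test |
|---|---|---|---|
| 60 | 1.0 | 10.4% | 5.4% |
| 60 | 2.0 | 25.7% | 7.0% |
| 30 | 1.0 | 7.5% | 5.6% |
| 30 | 2.0 | 15.6% | 7.3% |

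The simulated values at skewness 1 and 2 agree with the rough figures in step 2.

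**The case against.** The strongest objection concerns the null used above. If treatment changes nothing and baseline and week-12 values are exchangeable, the paired differences are symmetric however skewed activity itself is, and the signed-rank test is then valid. This is correct: differences of two exchangeable lognormals give 4.9% under the SAP rule at N=100.

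Correlated lognormals with equal means were also run (assumed baseline CV 40%, correlation 0.5 or 0.7, N=60 and 100, two sets of 3,000 datasets per setting). The SAP rule gives 4.4–5.5% when the spread is unchanged, 5.5–8.0% if the post-treatment CV rises to 48%, and about 9–20% if it rises to 60%. Marked inflation therefore needs the distribution to change shape while its mean stays put. That is plausible if some patients gain a lot and others lose a little, but the documents do not establish it.

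Three further points deserve weight:

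- In the endpoint's wording, the mean can be read as each patient's average over eligible days, so a population mean change is inferred from the protocol's t-test rather than spelled out. This leaves a conflict between p-value and interval possible, not certain. It also shows that the SAP should name its target.
- Protocol 9.5 describes the research as exploratory and without hypotheses, and Protocol 9.7 leaves details to the SAP. Even so, both documents set a two-sided 5% test, and replacing a named test is more than a detail.
- The SAP is to be signed before database closure, and the choice follows the shape of the data, not the p-value. It is not outcome shopping, and pre-testing costs nothing under normality (5.0%). The missing criterion remains.

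**Conclusion.** The concern holds. The contradiction between Protocol 9.7 and SAP 6.3.1 is plain from the text, and the decision rule cannot be reproduced as written. High confidence attaches to both.

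The inflation is real but conditional. For skewed changes with zero mean, the error rate rises from 5% to roughly 7% at skewness 0.5, 12–13% at 1.0 and 38% at 2.0 (N=100, Shapiro-Wilk assumed). It is absent for symmetric changes. No single error rate can be claimed, because the documents give no information on shape. The fixed t-test stays within 4.9–5.9% for skewness up to 2 at N=100. It is not exact in small, strongly skewed samples, but in every skewed setting in the tables above it is closer to 5% than the SAP rule.

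This should be corrected before the database is closed. The exploratory, single-arm design keeps it from being more serious.

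**What to change.** Replace the test sentence in SAP 6.3.1 with wording such as:

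> The change in mean daytime physical activity from the baseline wear period (before V2) to the wear period before V5 is tested with the two-sided one-sample t-test (alpha 0.05) and reported as mean change with 95% confidence interval, regardless of the observed distribution. The Wilcoxon signed-rank test on the same changes is a supportive sensitivity analysis.

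The test, the interval and the power statement then address the same quantity. If the sponsor prefers to keep a conditional rule, the SAP must at least acknowledge and justify the departure from Protocol 9.7, state the normality criterion and the variable it is applied to, and name the Wilcoxon test and the quantity it tests. That removes the ambiguity but not the inflation under skewness.

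The cost is one SAP sentence, with no new data, patients or procedures.

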6.3.2 Secondary Endpoints

For the secondary endpoints „change of FSS between baseline, during and after 12 weeks“ the difference between baseline and the respective follow-up visits will be calculated and

shown with 95% confidence intervals (95%-CI). This analysis will also be performed for the parameters daytime activity and sleep efficiency.

Furthermore for daytime activity, FSS and sleep efficiency 95%-CI will be provided at baseline, during the study and after 12 weeks.

The correlation between mean daytime physical activity and FSS will be analyzed for each visit and for the changes between baseline and follow-up visits using Spearman's rank correlation coefficient.

The proportion of patients achieving SVR12 will be calculated and shown with 95 % confidence interval.

6.3.3 Subgroup Analyses

According to the HEMATITE study protocol (version 1.0, 09/20/2016) „subgroup analyses will be provided for patients who achieve/do not achieve SVR12 after treatment with 3D regimen“. These analyses will be performed for ITT and mITT.

Daytime activity, FSS and sleep efficiency will be compared between following groups:

- Patients with Ribavirin vs. patients without Ribavirin at visit V2, V3, V4 and V5.
- Women vs. men at each visit.
- Patients with different fibrosis stages (F0, F1, F2 or F3) at each visit.
- Patients with different age categories (median split) at each visit.

Additionally for patients with GT1a vs. patients with GT1b FSS will be compared at each visit.

All statistical analyses will be performed by SPSS® for Windows, version 22.0.

7 Time table

The following temporary periods of time are planned:

| | |
|----------------------------------|------------------|
| Last patient out | April 2018 |
| Data input until | May 2018 |
| Cleanfile | June 2018 |
| Statistical analyses | Juli/August 2018 |
| Integrated Clinical Study Report | September 2018 |

Deviations from this plan because of unexpected occurrence are possible.

8 Planned tables for the statistical part

| Number | Items | Database/Variables |
|--|--|--|
| 1 Information to the study course | | |
| 1.1 | Enrolled/dropped out patients | Database 1 – Visit 1 (Day -28) |
| 1.2 | Study visits and study termination | Database 1 – Visit 1 (Day -28) – Visit 5 (Day 168, SVR12) |
| 1.3 | Patient eligibility criteria | Database 1 – Visit 1 (Day -28) |
| 2 Patients baseline characteristics | | |
| 2.1 | Demographics | Database 1 – Visit 1 (Day -28) |
| 2.2 | Medical history | Database 1 – Visit 1 (Day -28) |
| 2.3 | Fatigue severity scale (FSS) | Database 1 – Visit 1 (Day -28) |
| 2.4 | HCV history | Database 1 – Visit 1 (Day -28) |
| 2.5 | Vital signs | Database 1 – Visit 1 (Day -28) |
| 2.6 | Laboratory | Database 1 – Visit 1 (Day -28) |
| 2.7 | Smoking/alcohol status | Database 1 – Visit 1 (Day -28) |
| 2.8 | Activity tracker | Database 2 – Tracker data |
| 2.9 | Concomitant medication | Database 1 – Visit 1 (Day -28) |
| 3 Patients characteristics during study | | |
| 3.1 | Activity tracker | Database 2 – Tracker data |
| 3.2 | (S)AEs and concomitant medication | Database 1 – Visit 2 (Day 1) – Visit 5 (Day 168, SVR12) |
| 3.3 | Fatigue severity scale (FSS) | Database 1 – Visit 2 (Day 1) – Visit 5 (Day 168, SVR12) |
| 3.4 | Start of 3D regimen / 3D regimen | Database 1 – Visit 2 (Day 1) – Visit 4 (Day 84) |
| 3.5 | Vital signs | Database 1 – Visit 2 (Day 1) – Visit 5 (Day 168, SVR12) |
| 3.6 | Laboratory | Database 1 – Visit 2 (Day 1) – Visit 5 (Day 168, SVR12) |
| 3.7 | Physical examination | Database 1 – Visit 4 (Day 84) and Visit 5 (Day 168, SVR12) |
| 3.8 | Smoking/alcohol status | Database 1 – Visit 5 (Day 168, SVR12) |
| 4 Statistical analysis | | |
| 4.1 | Primary endpoint | Database 2 – Tracker data |
| 4.2 | Secondary endpoints – Change of parameters | Database 1 (visit data) and database 2 (tracker data) |
| 4.3 | Secondary endpoints - Correlations | Database 1 and database 2 |
| 4.4 | Secondary endpoints – Proportion of SVR12 | Database 1 |

| Number | Items | Database/Variables |
|----------------------------|--|---------------------------|
| 5 Subgroup analyses | | |
| 5.1 | Daytime activity, FSS and sleep efficiency for patients with/without Ribavirin | Database 1 and database 2 |
| 5.2 | Daytime activity, FSS and sleep efficiency for Women vs. men | Database 1 and database 2 |
| 5.3 | Daytime activity, FSS and sleep efficiency for patients with different fibrosis stages | Database 1 and database 2 |
| 5.4 | Daytime activity, FSS and sleep efficiency for patients with different age categories | Database 1 and database 2 |
| 5.5 | FSS for patients with GT1a vs. GT1b | Database 1 and database 2 |

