**Study Size:**

Approximately 100 patients in Switzerland will be enrolled.

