9.1.2 Description of Visits

Activity	Treatment Preparation	Treatment Phase				Follow up	
	V1	V2	V3	Phone Call	V4	Phone Call	V5
	Day -28	Day 1	Day 28	Day 56	Day 84	Day 140	Day 168 SVR12
Routinely assessed data required for this study							
Patient information and informed consent	X						
Inclusion/Exclusion Criteria check (Patient Selection)	X						
Demographics: Year of birth, ethnicity, sex	X						
HCV History (first diagnosis, date and source of infection, fibrosis stage)	X						
Medical History (including extrahepatic manifestation)	X						
HCV Viral load	X	X	X		X		X
Start the medication regimen		X					
Adverse events		X 	X		X		X 
Concomitant medication	X	X	X		X		X
Explain function and wearing of activity tracker	X						
Handing out the activity tracker	X						
Investigation of handling with the activity tracker		X	X		X		X
Reminder Call to start new cycle of wearing the activity tracker				X		X	
Collect activity tracker							X
FSS Questionnaire 	X	X	X		X		X

Additional data recorded in the CRF if routinely available							
Physical Exam	X				X		X
Vital signs (blood pressure, pulse, weight, height and body temp)	X	X	X		X		X
Smoking and Alcohol status	X						X
Laboratory	X	X	X		X		X
Treatment documentation (compliance)			X		X		
1: Capturing Adverse Events and Serious Adverse Events begins with the signature of the informed consent and stops 30 days after the last intake of the 3D regimen. 2: To be filled out at every visit by the patient himself and without any prior influence by the study personal.							

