## **10.0 Protection of Human Subjects**

This observational study will be run in compliance with local laws and regulations.

Notification/submission to the responsible regulatory authorities, Ethics Committee (EC) and/or Competent Authorities (CAs) will be done as required by local laws and regulations.

The investigator is responsible to ensure that written informed consent to use and/or disclose patients' anonymized health data will be obtained prior to patient inclusion.

To maintain patient confidentiality, no demographic data that can identify the patient will be collected (e.g. initials, date of birth) - only the patient age will be collected. In order to protect patient identity, a unique number will be assigned to each patient and related study records.

The study will be entirely financed by AbbVie AG. The patient will not be paid for his participation in the study.

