As described in the HEMATITTE study protocol (version V1.0, 09/20/2016) „... patients with Hepatitis C Virus (HCV) infection reported physical and mental fatigue as the most common symptom, highly impacting their overall quality of life. AASLD (American Association for the Study of Liver Diseases) and EASL (European Association for the Study of the Liver) guidelines therefore rate the treatment of HCV patients suffering from debilitating fatigue as a high priority. This cardinal symptom presents regardless of the stage of liver fibrosis and is difficult to quantify objectively. Similar to other potential reasons for physical fatigue, such as hepatic encephalopathy, increasing evidence suggests a direct viral impact on the central nervous system (CNS). Data demonstrating a longitudinal change of debilitating physical fatigue and increased daytime physical activity upon treatment with 3D regimen are missing to date and are anticipated by the Swiss scientific HCV community.

The rationale for this observational study is to observe the impact of therapy with 3D regimen on physical activity of HCV patients suffering from debilitating fatigue. Furthermore, this study supports the Swiss Hepatitis Strategy, which seeks for the elimination of viral hepatitis in Switzerland within the next 15 years by creating awareness for patients with extrahepatic manifestations.“

Patients included in this study applied the following criteria:

- Male or female, aged ≥ 18 years
- Treatment-naive
- Monoinfected with CHCV, GT 1 (confirmed within the last 36 months or at physicians discretion in case of risk factors)
- Non-cirrhotic (based on liver biopsy, fibroscan $\leq 9,6$ kPa and/or clinical signs)
- The decision to treat with 3D regimen is made by the physician in accordance with the local Swiss product label prior to any decision to approach the patient to participate in this study.
- Debilitating fatigue (FSS ≥ 4)
- Willing to participate in the study, and willing to wear an activity tracker.

Patients excluded from this study:

- With sources of fatigue other than HCV (especially, severe depression, cancer and hormonal disorders causing clinically significant fatigue).
- With conditions that do not allow to adhere to protocol and use of the device at investigator's discretion.
- Being wheelchair dependent.

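### SAP 6.3.3 splits age at the median although age is collected as a number; in these exploratory comparisons this gives up roughly a quarter to a third of the information on a linear age relation

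*SAP*

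**What the plan says.** SAP 6.3.3 states that "Daytime activity, FSS and sleep efficiency will be compared between following groups" and then lists the groupings. One of them is "Patients with different age categories (median split) at each visit". In SAP section 8, planned table 5.4 repeats it: "Daytime activity, FSS and sleep efficiency for patients with different age categories". The SAP gives no cut-point in years, no reason for the split, and no rule for a patient whose age equals the median. It names no test, model or interval for these comparisons.

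Age itself is held ungrouped. The visit table in protocol 9.1.2 lists "Demographics: Year of birth, ethnicity, sex", and protocol 10.0 says "only the patient age will be collected". Either source gives age as a number of years. On the age distribution, the only information is the lower limit for eligibility: "Male or female, aged ≥ 18 years".

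The protocol (9.7) plans subgroup analyses only by SVR12 status. It describes the research as exploratory, without pre-specified hypotheses (9.5).

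**The concern.** A median split replaces each patient's age by one of two labels. Two patients a year apart on either side of the median count as different, and two patients decades apart on the same side count as alike. If activity, fatigue or sleep changes steadily with age, the split estimates that relation less precisely than the collected data allow. If the comparison is tested, a real gradient is more easily missed.

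The second cost is comparability. The boundary between younger and older is the median of this sample, so it is not known until the data are in. Another cohort will have a different one, and the two contrasts then do not describe the same thing.

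**Working it through.** **The plan's own figure.** The documents give no power or precision for any age comparison. The only power statement is in protocol 9.5 for the primary variable: 100 patients, effect size 0.29, two-sided one-sample t-test at 5%, 80% power. The noncentrality is 0.29 × √100 = 2.9. The exact power from the noncentral t distribution is 81.9%, and the normal approximation gives Φ(2.9 − 1.96) = 82.6%. The stated figure is reproduced to within 2 points. It has no bearing on age.

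**Inputs for the age question**
- Planned size: 100 ("Approximately 100 patients in Switzerland will be enrolled").
- Assumed, because the documents are silent: the shape of the age distribution, a linear relation with age, the correlation r, and the number analysed. I use n = 90 for illustration because SAP 5.2 analyses the endpoints in patients who attend all five visits. No dropout rate is given.

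**Information kept by the split.** Let X be age with median m, and let G = 1 if X > m. Then Cov(X, G) = ½·E|X − m| and SD(G) = ½, so corr(X, G) = E|X − m| / SD(X). For a linear relation, corr(outcome, G) = r × corr(X, G), and the share of information kept is corr(X, G)².
- Normal age: corr = √(2/π) = 0.798, share kept 2/π = 0.637, loss 36%.
- Uniform age: corr = (1/2)/(1/√3) = 0.866, share kept 0.75, loss 25%.
- Other shapes, by simulation:

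| Assumed age shape | Share kept | Loss |
|---|---|---|
| Normal, mean 50, SD 12, cut at 18 | 0.643 | 36% |
| Two peaks, equal mix of N(35, 6) and N(58, 6) | 0.803 | 20% |
| Right-skewed, gamma shape 4 | 0.594 | 41% |
| Right-skewed, gamma shape 2 | 0.553 | 45% |

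For normal age, 100 split patients carry the linear information of about 64 unsplit ones. Put the other way, 100/0.637 = 157 split patients would be needed to match 100.

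**Effect on power.** By Fisher's z, power = Φ(atanh(r)·√(n − 3) − 1.96), two-sided 5%.
- n = 90, r = 0.30, continuous age: 0.3095 × 9.327 − 1.96 = 0.927, power 82%.
- Same, split, normal age: r becomes 0.30 × 0.798 = 0.239; 0.2441 × 9.327 − 1.96 = 0.317, power 62%.
- Same, split, uniform age: r becomes 0.260, power 70%.
- n = 90, r = 0.25: 66% continuous; 47% after the split for normal age, 54% for uniform.
- n = 100, r = 0.30: 86% continuous; 67% after the split for normal age.
- n = 100: a correlation of 0.277 has 80% power with continuous age, and about 60% (normal) or 67% (uniform) after the split.

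The continuous-age figures apply to a regression slope or Pearson correlation. A Spearman coefficient gives up a little of this advantage when the data are normal.

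**The case against.** The strongest reply is that this hardly matters. No objective or endpoint concerns age, the study is exploratory, and the data are to be summarised mainly descriptively. The SAP names no test for the comparison, so power figures refer to a hypothesis the study does not set out to test. Two groups of similar size make a table that reads like the ones for sex and ribavirin, and they assume no linear relation. The size of the loss depends on a distribution and a correlation that the documents do not give.

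Most of this stands, and it sets the weight of the point: minor, with the numbers given as ranges under stated assumptions. It also means the split cannot be called pointless. What it does not answer is precision. Describing how an outcome varies with age is also done better with the ages themselves, and the tables can stay.

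A reader might go further in three ways that the documents do not support.
- *That a data-driven cut biases the result.* The median depends on ages alone and not on outcomes, and the rule is written down in advance. It does not inflate the type I error.
- *That a patient could count as younger in the ITT and older in the mITT.* The sentence applying analyses to both populations directly follows the SVR12 subgroup, before the list that contains age. Nothing says that the median would be recomputed in each population.
- *That fibrosis is mishandled in the same way.* The SAP lists "Patients with different fibrosis stages (F0, F1, F2 or F3) at each visit" but specifies no omnibus test, so a charge of wasted degrees of freedom is aimed at an analysis that is not in the plan. An ordered analysis is unspecified rather than excluded, and separate stages avoid assuming an evenly spaced gradient.

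**Conclusion.** The point holds for age, as a minor one. The SAP prescribes a median split where the ungrouped value is available, and it plans no continuous analysis beside it. Under an approximately linear relation the loss of information is 36% for normal age and 25% for uniform age, within about 20% to 45% over plausible shapes. The fall in power from 82% to 62% is an illustration for normal age with assumed r = 0.30 and n = 90, and it is not a property of the plan. The sample-specific cut also limits comparison with other cohorts. The validity of the comparison and the primary endpoint, with its test and its stated power, are untouched.

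**What to change.** In SAP 6.3.3 and planned table 5.4, make continuous age the main analysis for each of the three outcomes at each visit where it is measured. Use either a Spearman coefficient, which SAP 6.3.2 already uses for activity and FSS, or a regression slope per 10 years with a 95% confidence interval. Keep the median-split groups as a descriptive display. State the rule for the cut and the group that takes patients exactly at the median, since age comes in whole years, and report the cut-point in years.

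Optionally, because no test is named for fibrosis, add a trend summary over F0 to F3 beside the stage-wise results.

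The cost is a few lines of SAP text and one revised table shell, with no new data and no additional patients. The downside is small: a slope or coefficient is less simple to read than two group means, and a slope assumes approximate linearity.
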